#### 10 ADVERSE EVENTS

### 10.1 Monitoring, Recording and Reporting of Adverse Events

An AE is any noxious, unintended, or untoward medical occurrence that may appear or worsen in a subject during the course of a study. It may be a new intercurrent illness, a worsening concomitant illness, an injury, or any concomitant impairment of the subject's health, including laboratory test values (as specified by the criteria in Section 10.3), regardless of etiology. Any worsening (ie, any clinically significant adverse change in the frequency or intensity of a pre-existing condition) should be considered an AE. A diagnosis or syndrome should be recorded on the AE page of the CRF rather than the individual signs or symptoms of the diagnosis or syndrome.

Abuse, withdrawal, sensitivity, or toxicity to an investigational product should be reported as an AE. Overdose, accidental or intentional, whether or not it is associated with an AE should be reported on the overdose CRF. (See Section 7.2.7.10 for the definition of overdose). Any sequela of an accidental or intentional overdose of an investigational product (IP) which meets the definition of an adverse event, should be reported as an AE on the CRF. If the sequela of an overdose meets serious criteria, then it must be marked as serious on the CRF. The overdose itself should not be reported as an AE.

In the event of overdose, the subject should be monitored as appropriate and should receive supportive measures as necessary. There is no known specific antidote for CC-95251 overdose. Actual treatment should depend on the severity of the clinical situation and the judgment and experience of the treating physician.

All subjects will be monitored for AEs during the study. Assessments may include monitoring of any or all of the following parameters: the subject's clinical symptoms, laboratory, pathological, radiological or surgical findings, physical examination findings, or findings from other tests and/or procedures.

All AEs will be recorded by the Investigator from the time the subject signs informed consent until after the last dose of study drug. In addition, SAEs made known to the Investigator at any time thereafter that are suspected of being related to IP will be reported until such SAEs have recovered (returned to baseline), recovered with sequelae, or death (due to the SAE). All adverse events (serious/non-serious) will be recorded on the CRF and in the subject's source documents. Refer to Section 10.5 for instructions on how to report SAEs to Drug Safety.

Subjects will be followed for all SAEs, and AEs (SAEs and non-serious AEs) associated with confirmed or suspected SARS-CoV-2 infection until resolution, the condition stabilizes, the event is otherwise explained, the event is deemed irreversible, the subject is lost to follow-up, or for suspected cases, until SARS-CoV-2 infection is ruled out.

#### 10.2 Evaluation of Adverse Events

A qualified Investigator will evaluate all adverse events as to:

### 10.2.1 Seriousness

An SAE is any AE occurring at any dose that:

- Results in death;
- Is life-threatening (ie, in the opinion of the Investigator, the subject is at immediate risk of death from the AE);
- Requires inpatient hospitalization or prolongation of existing hospitalization (hospitalization is defined as an inpatient admission, regardless of length of stay);
- Results in persistent or significant disability/incapacity (a substantial disruption of the subject's ability to conduct normal life functions);
- Is a congenital anomaly/birth defect;
- Constitutes an important medical event.

Important medical events are defined as those occurrences that may not be immediately life-threatening or result in death, hospitalization, or disability, but may jeopardize the subject or require medical or surgical intervention to prevent one of the other outcomes listed above. Medical and scientific judgment should be exercised in deciding whether such an AE should be considered serious.

Events **not considered** to be SAEs are hospitalizations for:

- a standard procedure for protocol therapy administration. However, hospitalization or prolonged hospitalization for a complication of therapy administration will be reported as an SAE.
- routine treatment or monitoring of the studied indication not associated with any deterioration in condition.
- the administration of blood or platelet transfusion as routine treatment of studied indication. However, hospitalization or prolonged hospitalization for a complication of such transfusion remains a reportable SAE.

- a procedure for protocol/disease-related investigations (eg, surgery, scans, endoscopy, sampling for laboratory tests, bone marrow sampling). However, hospitalization or prolonged hospitalization for a complication of such procedures remains a reportable SAE.
- hospitalization or prolongation of hospitalization for technical, practical, or social reasons, in absence of an AE.
- a procedure that is planned (ie, planned prior to start of treatment on study); must be documented in the source document and the CRF. Hospitalization or prolonged hospitalization for a complication remains a reportable SAE.
- an elective treatment of or an elective procedure for a pre-existing condition, unrelated to the studied indication, that has not worsened from baseline.
- emergency outpatient treatment or observation that does not result in admission, unless fulfilling other seriousness criteria above.

For each AE, the Investigator will provide information on severity, start and stop dates, relationship to the IP, action taken regarding the IP, and outcome.

## 10.2.2 Severity/Intensity

For each AE, the Investigator must assess the severity/ intensity of the event.

The severity/intensity of AEs will be graded based upon the subject's symptoms according to the current active minor version of the Common Terminology Criteria for Adverse Events (CTCAE, Version 5.0);

 ${\it https://ctep.cancer.gov/protocolDevelopment/electronic\_applications/ctc.htm}$ 

AEs that are not defined in the CTCAE should be evaluated for severity/intensity according to the following scale:

- Grade 1 = Mild transient or mild discomfort; no limitation in activity; no medical intervention/therapy required
- Grade 2 = Moderate mild to moderate limitation in activity, some assistance may be needed; no or minimal medical intervention/therapy required
- Grade 3 = Severe marked limitation in activity, some assistance usually required; medical intervention/therapy required, hospitalization is possible
- Grade 4 = Life-threatening extreme limitation in activity, significant assistance required; significant medical intervention/therapy required, hospitalization or hospice care probable
- Grade 5 = Death the event results in death

The term "severe" is often used to describe the intensity of a specific event (as in mild, moderate or severe myocardial infarction); the event itself, however, may be of relatively minor medical significance (such as severe headache). This criterion is *not* the same as "serious" which is based on subject/event *outcome* or *action* criteria associated with events that pose a threat to a subject's life or functioning.

Seriousness, not severity, serves as a guide for defining regulatory obligations.

## 10.2.3 Causality

The Investigator must determine the relationship between the administration of the IP and the occurrence of an AE as Not Suspected or Suspected as defined below:

Not suspected: a causal relationship of the adverse event to IP administration is

unlikely or remote, or other medications, therapeutic interventions, or underlying conditions provide a sufficient

explanation for the observed event.

Suspected: there is a reasonable possibility that the administration of IP

caused the adverse event. 'Reasonable possibility' means there is evidence to suggest a causal relationship between the IP and

the adverse event.

Causality should be assessed and provided for each AE based on currently available information. Causality is to be reassessed and provided as additional information becomes available.

If an event is assessed as suspected of being related to a comparator, ancillary or additional IP that has not been manufactured or provided by the Sponsor, please provide the name of the manufacturer when reporting the event.

#### 10.2.4 Duration

For each AE, the Investigator will provide a record of the start and stop dates of the event.

#### 10.2.5 Action Taken

The Investigator will report the action taken with IP as a result of each AE, as applicable (eg, discontinuation, interruption, or dose reduction of IP, as appropriate) and report if concomitant and/or additional treatments were given for the event.

#### 10.2.6 Outcome

The Investigator will report the outcome of the event for each AE.

All SAEs that have not resolved upon discontinuation of the subject's participation in the study must be followed until recovered (returned to baseline), recovered with sequelae, or death (due to the SAE).

## 10.3 Abnormal Laboratory Values

An abnormal laboratory value is considered to be an AE if the abnormality:

- results in discontinuation from the study;
- requires treatment, modification/interruption of IP dose, or any other therapeutic intervention; or
- is judged to be of significant clinical importance, eg, one that indicates a new disease process and/or organ toxicity, or is an exacerbation or worsening of an existing condition.

Regardless of severity grade, only laboratory abnormalities that fulfill a seriousness criterion need to be documented as a serious adverse event.

If a laboratory abnormality is one component of a diagnosis or syndrome, then only the diagnosis or syndrome should be recorded as the AE. If the abnormality was not a part of a diagnosis or syndrome, then the laboratory abnormality should be recorded as the AE. If possible, the laboratory abnormality should be recorded as a medical term and not simply as an abnormal laboratory result (eg, record thrombocytopenia rather than decreased platelets).

## 10.4 Pregnancy

All pregnancies or suspected pregnancies occurring in either a SCBP or partner of childbearing potential of a subject are immediately reportable events.

The exposure of any pregnant individual (eg, caregiver, pharmacist, study coordinator, or monitor) to IP is also an immediately reportable event.

### 10.4.1 Subjects of Childbearing Potential

Pregnancies and suspected pregnancies (including elevated βhCG or positive pregnancy test in a SCBP regardless of disease state) occurring while the subject is on IP, or within of the subject's last dose of CC-95251 or 6 months of the subject's last dose of azacitidine (or longer if required by local regulations), are considered immediately reportable events. Investigational product is to be discontinued immediately. The pregnancy, suspected pregnancy, or positive pregnancy test must be reported to the Sponsor's Drug Safety immediately by email, phone or facsimile, or other appropriate method, using the Pregnancy Initial Report Form, or approved equivalent form.

The SCBP may be referred to an obstetrician-gynecologist or another appropriate healthcare professional for further evaluation.

The Investigator will follow the SCBP until completion of the pregnancy and must notify the Sponsor's Drug Safety immediately about the outcome of the pregnancy (either normal or abnormal outcome) using the Pregnancy Follow-up Report Form, or approved equivalent form.

If the outcome of the pregnancy was abnormal (eg, spontaneous abortion), the Investigator should report the abnormal outcome as an AE. If the abnormal outcome meets any of the serious criteria, it must be reported as an SAE to the Sponsor's Drug Safety within 24 hours of the Investigator's knowledge of the event.

All neonatal deaths that occur within 28 days of birth should be reported, without regard to causality, as an SAE. In addition, any infant death after 28 days that the Investigator suspects is related to the in utero exposure to the IP should also be reported as an SAE to the Sponsor's Drug Safety within 24 hours of the Investigator's knowledge of the event.

## 10.4.2 Subjects Who Are Able to Impregnate Their Partner

If a partner of childbearing potential of a subject taking IP becomes pregnant, the subject taking IP should notify the Investigator, and the pregnant partner should be advised to call their healthcare provider immediately.

### 10.5 Reporting of Serious Adverse Events

Any AE that meets any serious criterion requires reporting as an SAE within 24 hours of the Investigator's knowledge of the event. This instruction pertains to initial SAE reports as well as any follow-up reports.

This requirement applies to all SAEs (regardless of relationship to IP) that occur during the study (from the time the subject signs informed consent until after the last dose of IP) or any SAE made known to the Investigator at any time thereafter that are suspected of being related to IP. Serious adverse events occurring prior to treatment (after signing the ICF) are to be recorded within the CRF, but do not require reporting to the Sponsor's Drug Safety.

Where required by local legislation, the Investigator is responsible for informing the Institutional Review Board/Ethics Committee (IRB/EC) of the SAE and providing them with all relevant initial and follow-up information about the event. The Investigator must keep copies of all SAE information on file including correspondence with the Sponsor and the IRB/EC.

The SAE is recorded within the CRF, and the data is transmitted electronically to the Sponsor's Drug Safety. In the event electronic transmission is not available, a paper SAE Report Form will be completed and sent directly to the Sponsor's Drug Safety, ensuring the event is recorded on the CRF as well.

#### 10.6 Expedited Reporting of Adverse Events

For the purpose of regulatory reporting, the Sponsor's Drug Safety will determine the expectedness of events suspected of being related to CC-95251 based on the Investigator Brochure and azacitidine based on SmPC.

In the United States, expedited reports sent to the FDA by the sponsor based on the reasonable possibility threshold are known as 'IND safety reports' and will be reported in accordance with 21 CFR 312.32.

For reporting to the FDA, events that are not suspected to be causally related to CC-95251 and azacitidine by the sponsor will not be considered adverse reactions.

For countries within the European Economic Area (EEA), the Sponsor or its authorized representative will report in an expedited manner to Regulatory Authorities and Ethics Committees concerned, suspected unexpected serious adverse reactions (SUSARs) in accordance with Directive 2001/20/EC and the Detailed Guidance on collection, verification and presentation of adverse reaction reports arising from clinical trials on investigational products for human use (ENTR/CT3) and also in accordance with country-specific requirements.

The Sponsor or its authorized representative shall notify the Investigator of the following information:

- Any AE suspected of being related to the use of IP in this study or in other studies that is both serious and unexpected (ie, SUSAR);
- Any finding from tests in laboratory animals that suggests a significant risk for human subjects including reports of mutagenicity, teratogenicity, or carcinogenicity.

Where required by local legislation, the Investigator shall notify his/her IRB/EC promptly of these new serious and unexpected AE(s) or significant risks to subjects.

The Investigator must keep copies of all pertinent safety information on file including correspondence with the IRB/EC. (See Section 13.3 for record retention information).

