### 7.1.3 Venetoclax

[figure not shown]
Venetoclax will be supplied or obtained according to local clinical study agreement and in accordance with local guidelines. When provided by the Sponsor, venetoclax will be supplied as tablets in 10 mg, 50 mg, and 100 mg blister/bottles for administration. Material supplied by the Sponsor will be labeled appropriately for investigational use per the regulations of the relevant country health authority.

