### 7.2.7.10 Definition of Overdose

Overdose, as defined for this protocol, refers to CC-95251, azacitidine, and venetoclax.

On a per dose basis, an overdose is defined as the following amount over the protocol-specified dose of CC-95251 or azacitidine or venetoclax assigned to a given subject, regardless of any associated AEs or sequelae:

Complete data about drug administration, including any overdose, regardless of whether the overdose was accidental or intentional, should be reported in the case report form. Refer to Section 10.1 for the reporting of adverse events associated with overdose.

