## 7.5 Investigational Product Accountability and Disposal

Accountability for study drug that is administrated during the course of the study is the responsibility of the Investigator or designee. Investigational clinical supplies must be received by a designated person at the clinical site and kept in a secure and temperature-controlled location. For CC-95251, azacitidine, and venetoclax, the investigational site must maintain accurate records demonstrating dates and amounts of study drug received or obtained from the pharmacy, to whom it was administered (subject-by-subject accounting), and accounts of any vials accidentally or deliberately damaged and/or returned to the Sponsor.

The Sponsor (or designee) will review with the Investigator and relevant site personnel the process for documenting receipt of IP, as well as procedures for accounting, reconciling IP, and documenting this process.

The Sponsor (or designee) will review with the Investigator and relevant site personnel the process for IP return, disposal, and/or destruction including responsibilities for the site versus the Sponsor (or designee).

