## 7.6 Investigational Product Compliance

Only the pharmacist or Investigator's designee will dispense CC-95251 and azacitidine. A record of the total dose (and number of vials used) of CC-95251 and azacitidine administered to each subject must be maintained.

Protocol CA059-001 Amendment 3.0

930197534 2.0

Approved v2.0

The pharmacist or Investigator's designee will document the doses dispensed/administered in the appropriate study records and the appropriate eCRF. Study intervention compliance will be periodically monitored by drug accountability, including the review of dosing diary cards. Drug accountability should be reviewed by the study site staff at each visit to confirm treatment compliance. Study sites should discuss discrepancies with the subject at each on-treatment study visit.

- When subjects are dosed at the site, they will receive study intervention directly from the investigator or designee, under medical supervision. The date and time of each dose administered in the clinic will be recorded in the source documents and recorded in the electronic case report form (eCRF). The dose of study intervention and study subject identification will be confirmed at the time of dosing by a member of the study site staff other than the person administering the study intervention.
- When subjects self-administer venetoclax at home, compliance with study intervention will be assessed at each visit. Compliance will be assessed by direct questioning, and counting returned tablets during the site visits, and documented in the source documents and relevant form. Deviation(s) from the prescribed dosage regimen should be recorded in the eCRF.
- Accountability records of study interventions in respective sub-protocols dispensed and administered to each subject must be maintained and reconciled with study intervention and compliance records. Intervention start and stop dates, including dates for intervention delays and/or dose reductions, will also be recorded in the eCRF.

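### Section 10.6 was not extended to venetoclax: as written, an event the sponsor attributes to venetoclax alone is not an adverse reaction for FDA reporting

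*Combined protocol and SAP*

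**What the plan says.** Section 10.6 governs what the sponsor does with events once they have been reported to it. Four parts matter here.

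- **Expectedness.** For regulatory reporting, the sponsor's Drug Safety group determines the "expectedness of events suspected of being related to CC-95251 based on the Investigator Brochure and azacitidine based on SmPC". No reference is given for venetoclax.
- **FDA, general sentence.** IND safety reports are described as "expedited reports sent to the FDA by the sponsor based on the reasonable possibility threshold", to be made under 21 CFR 312.32. No drug is named.
- **FDA, specific sentence.** The next sentence, which is limited to US reporting, states that "events that are not suspected to be causally related to CC-95251 and azacitidine by the sponsor will not be considered adverse reactions".
- **Other routes.** The paragraph on SUSARs in the European Economic Area names no drug. Investigators are to be told of "Any AE suspected of being related to the use of IP in this study or in other studies that is both serious and unexpected".

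Venetoclax does not appear in the section. Elsewhere the current text treats it as a study drug:

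- The Study Treatments part of the Protocol Summary gives it daily in the triple combination cohorts.
- Table 1 (Section 1.4.2) gives it its own study-intervention heading.
- Section 7.1.3 describes it among the investigational products: "Material supplied by the Sponsor will be labeled appropriately for investigational use per the regulations of the relevant country health authority".
- Section 7.2.7.10: "Overdose, as defined for this protocol, refers to CC-95251, azacitidine, and venetoclax".
- Section 7.5: "For CC-95251, azacitidine, and venetoclax, the investigational site must maintain accurate records demonstrating dates and amounts of study drug received".
- Section 7.6: "When subjects self-administer venetoclax at home, compliance with study intervention will be assessed at each visit".

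**The concern.** The specific FDA sentence is an operative rule: it settles which events count as adverse reactions for that purpose. It lists two of the three drugs given in the triplet. A serious event that the sponsor judges to be caused by venetoclax, and by neither of the other two drugs, is on the literal text not an adverse reaction for FDA reporting.

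Such an attribution is not far-fetched. Table 1 lists risks for venetoclax separately, serious and fatal infections among them, and the protocol hospitalizes triplet subjects during venetoclax ramp-up because of the risk of tumor lysis syndrome. Drug Safety staff should not have to choose between a general sentence that would take such an event in and a more specific one, next to it, that leaves it out.

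The missing expectedness reference is a lesser matter. It leaves unstated which document decides whether a venetoclax-related event is unexpected. That judgement is needed for SUSAR reporting. It is also needed for investigator notification as far as *IP* covers venetoclax, and the protocol is not uniform on this: Section 3.1.5.2 attaches the term to CC-95251, while Sections 7.1 and 7.5 use it more widely.

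**Working it through.** There is no figure to reproduce. The check compares texts and then works through one logical case.

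**Step 1: which drugs each provision covers.**

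| Provision | CC-95251 | Azacitidine | Venetoclax |
|---|---|---|---|
| 10.6, expectedness reference | Investigator Brochure | SmPC | none stated |
| 10.6, specific FDA sentence | named | named | not named |
| 7.2.7.10, overdose | named | named | named |
| 7.5, accountability | named | named | named |
| 7.1, product descriptions | 7.1.1 | 7.1.2 | 7.1.3 |

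Section 10.6 covers 2 of 3 drugs in both places. The other provisions cover 3 of 3. The text of 10.6 shows no blacked-out words or gap at either place that could hide a reference to venetoclax.

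**Step 2: does the ambiguous *and* rescue the sentence?** Write C, A and V for the sponsor suspecting a causal relation to CC-95251, azacitidine and venetoclax. Take an event attributed to venetoclax alone: C = no, A = no, V = yes.

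- *Reading 1, either drug suffices.* An event is excluded if it is suspected of neither C nor A. Here both are no, so it is excluded.
- *Reading 2, both drugs required.* An event is excluded unless both C and A are suspected. Here neither is, so it is excluded.

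The result is the same on both readings, so the point does not depend on which was meant.

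**Step 3: does other text cure it?**

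- The general FDA sentence and the European paragraph name no drug. They could include a venetoclax-only event, but they do not override the specific sentence.
- Section 10.2.3 foresees attribution to an additional product that the sponsor neither made nor provided. It asks only for the manufacturer's name, and it does not reach venetoclax that the sponsor provides, which Section 7.1.3 allows for.
- Section 10.5 brings every SAE to the sponsor within 24 hours of the investigator's knowledge, whatever its relation to treatment, apart from SAEs before first treatment, which are only recorded. This secures the report to the sponsor, not the sponsor's later classification for the FDA.
- Section 9.10 describes sponsor processes for submitting individual reports, without naming a drug or a reference document.

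None of these removes the conflict.

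**The case against.** The strongest reply is that nothing would go wrong in practice. The sponsor has committed to 21 CFR 312.32 in general terms, receives SAEs regardless of attribution, and would presumably report a venetoclax-related reaction despite the wording. That may be so, and it is why the point is minor. But it amounts to relying on staff to disregard a sentence of the protocol.

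It might also be said that venetoclax was left out because it is a marketed drug. That does not explain the omission. Azacitidine is marketed too, is supplied on the same terms (Sections 7.1.2 and 7.1.3), and is named in both sentences.

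Several stronger readings are tempting and should be resisted.

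- *A breach of FDA rules.* The content of 21 CFR 312.32 is not in the documents, so they show only an internal conflict.
- *A weakened pausing rule.* Section 7.2.7 refers to unexpected treatment-related SAEs, so a reader might infer that the missing reference undermines it. But pausing is decided by the Safety Review Committee, the expectedness sentence in 10.6 is confined to regulatory reporting, and Section 9.9.1 restates the pausing rule without the word *unexpected*.
- *An indeterminable venetoclax reference.* The protocol cites both a package insert and an SmPC for venetoclax, but it also cites both kinds of label for azacitidine and still uses the SmPC in 10.6. The most that can be said is that the venetoclax reference is not stated.
- *Exclusion of events related to CC-95251 alone.* Reading 2 would produce this, but it is not a plausible intention and the point does not need it.

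**Conclusion.** The point stands as a minor one. Section 10.6 was not brought into line with the triplet, and its specific FDA sentence gives the wrong result for one class of event: those in the Part A triplet or Part D that the sponsor attributes to venetoclax alone. The omission is certain on the text. How often such events will occur cannot be estimated from the documents. The unstated expectedness reference is missing detail and would not be a finding on its own; it bears on any venetoclax-suspected event for which expectedness must be judged.

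The conclusion rests on reading the sentence as written and on venetoclax being a study intervention, which the protocol says in several places. It does not extend to data collection, 24-hour SAE reporting to the sponsor (10.5) or the tabulation of treatment-related AEs and SAEs (9.7). None of these is shown to be affected.

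**What to change.** In the specific FDA sentence of Section 10.6, replace the two-drug list with *any study intervention (CC-95251, azacitidine or venetoclax)*. This brings in venetoclax-only events, agrees with the preceding sentence, and removes the ambiguity of *and*.

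As an accompanying edit, add the expectedness reference for venetoclax to the expectedness sentence, in the same form as for the other two drugs. The sponsor should choose the document.

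The cost is two sentences in one section and some additional expedited-reporting assessments, number unknown. Data collection, analysis and patient management do not change.
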